### 5.4 Exit criteria

1) Patients request to drop out; 2) the cycle is cancelled due to low ovarian response or premature ovulation; 3) actual treatment deviates from the protocol; 4) patients lost follow-up.

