c. Oocyte retrieval, luteal support and embryo transfer: oocyte recovery is performed 34 to 38 hour after the trigger. Luteal support is provided on the day of oocyte retrieval, with vaginal micronized progesterone capsules (600mg/day) combined with oral dydrogesterone (30mg/day) until the pregnancy test. With the use of conventional IVF or ICSI fertilization, 1 to 2 cleavage stage embryos or day 5 blastocysts are transferred to the uterus, and the rest available embryos are cryopreserved.

d. If fresh embryo transfer is cancelled due to medical reasons, pregnancy outcome of the first thawed embryo transfer is collected. The endometrial preparation, thawed embryo transfer and luteal support are based on the routine operation.

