#### 5.8.7 Follow-up:

A total of three visits are followed up during the treatment procedure.

a. At the 14th day after embryo transfer: to record urinary pregnancy test, serum HCG and progesterone level.

If pregnancy test is positive, the following follow-up continues, otherwise it discontinues.

b. Four to five weeks after embryo transfer: to perform transvaginal ultrasound. Clinical pregnancy is defined as a gestational sac and fetal heart beat detected on ultrasound.

c. At 12 weeks' gestation: to perform ultrasound. Ongoing pregnancy is defined as live fetuses detected on ultrasound.

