#### 7.1 Data Analysis Set:

Full Analysis Set (FAS): the FAS include all randomized subjects receiving treatment at least once. According to the intent-to-treat population (ITT) principle, all randomized cases accepting intervention at least once should be analyzed.

Safety Set (SS): all randomized subjects accepting intervention at least once and receiving post-treatment safety evaluation at least once should be included in the SS. SS is the safety evaluation population for this trial.

Per-protocol population set (PPS): all subjects in the FAS without major protocol violation will be included. Major protocol violation should be defined in the statistical analysis plan before database locking and study unblinding. Subjects will be analyzed based on the treatment.

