#### 7.2 Analysis of primary indicator and secondary indicators:

Analysis of primary indicator: the two-sample rate test is used to compare the ongoing pregnancy rate at 12 weeks' gestation in the treatment group and the control group. Categorical variable is compared between groups using Pearson chi-squared test or Fisher's exact probabilistic method. Based on the FAS, the primary endpoint calculates the ongoing pregnancy rate at 12 weeks' gestation and its 95% confidence interval. Logistic regression is used to analyze the baseline effects, and the adjusted factors included age, infertility length, BMI, AMH, AFC, ovulation stimulation protocol, etc.

Analysis of secondary indicators: measurement data are compared using independent sample test or nonparametric analysis, and categorical variables are compared using Pearson chi-squared test or Fisher's exact probabilistic method between groups. Measurement data are analyzed by covariance analysis, and qualitative indicators are analyzed by Logistic regression to evaluate the baseline effects. Adjusted factors refer to the analysis of primary indicators.

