### 7.4.4 Data audit and database locking

After all questions of the data in the system are resolved, the principal investigator, statistician and data administrator first review the data and determine the association of adverse events and study, then determine the analyzed data set, last lock the audited data without any change. If there is any question after the database lock, it should be corrected in the statistical analysis process, and be recorded in detail.

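### Section 5.4 makes treatment deviation and cycle cancellation exits without saying that outcome collection continues, although the primary FAS analysis needs those outcomes; the FAS also leaves out randomised women who never start

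*Combined protocol and SAP*

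**What the plan says.** Section 5.4 gives four exit reasons: the patient's request, two described as "2) the cycle is cancelled due to low ovarian response or premature ovulation; 3) actual treatment deviates from the protocol", and loss to follow-up. It does not define exit, grade deviations by importance, or say what happens to data collection afterwards.

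Section 7.1 defines the analysis sets without reference to exit. For the full analysis set, "the FAS include all randomized subjects receiving treatment at least once". Under the intention-to-treat principle, "all randomized cases accepting intervention at least once should be analyzed". For the per-protocol set, "all subjects in the FAS without major protocol violation will be included", with major violations to be defined before database lock. Section 7.2 names the set for the main result: "Based on the FAS, the primary endpoint calculates the ongoing pregnancy rate".

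The only rule on continuing or stopping follow-up is in section 5.8.7: "If pregnancy test is positive, the following follow-up continues, otherwise it discontinues". Section 5.8.5(d) adds that, when the fresh transfer is cancelled for medical reasons, the outcome of the first thawed transfer is collected. At data review under section 7.4.4 the team is to "then determine the analyzed data set, last lock the audited data without any change". No section says how an unknown primary outcome is counted.

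**The concern.** A woman whose treatment deviates is an exit under section 5.4, yet sections 7.1 and 7.2 count her in the primary denominator, where she needs a 12-week outcome. Because the neighbouring reasons are dropping out and loss to follow-up, site staff could naturally take exit to mean leaving the study. Her outcome might then not be sought, and the analyst would have no rule for scoring her.

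Such losses need not be balanced between arms. No blinding procedure is described (section 7.1 mentions unblinding, but nothing sets up a blind), the investigator opens the envelope (section 5.5), and the arms take 4 pills against 1 tablet a day (section 4). For the same reason, failing to start can depend on the allocated arm, and the FAS removes exactly those women. Section 5.1 also intends to calculate the later sample size from these preliminary results, so the rates matter beyond this stage.

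**Working it through.** **Step 1: what each exit reason does to the primary outcome.**

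- *Request to drop out.* The outcome can still be obtained if the woman allows follow-up. The plan does not separate stopping the product from refusing follow-up.
- *Cycle cancelled for low response or premature ovulation.* If no transfer follows, the result is largely known: no ongoing pregnancy. What is missing is a sentence saying that it is scored so.
- *Treatment deviation.* This is the main exposure. As worded it could cover a departure from the daily supplement regimen, or from a procedural window such as "oocyte recovery is performed 34 to 38 hour after the trigger" (section 5.8.5(c)). The plan does not say that it is applied to such cases, but nothing excludes them. Such a woman can still have a transfer and conceive.
- *Loss to follow-up.* Continued collection cannot help, so a missing-outcome rule is needed.

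**Step 2: inputs for scale.** Section 5.1 gives 40 women per arm. The plan states no control rate, effect size or exit rate, so it has no figure to reproduce. All counts and rates below are assumptions.

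**Step 3: value of one unknown outcome.** 1/40 = 2.5 percentage points of an arm's rate.

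**Step 4: bounds with k unknown outcomes in each arm and equal known pregnancies.** The difference is bounded by ±k/40:

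| k per arm | Bound on difference |
|---|---|
| 1 | ±2.5 points |
| 2 | ±5.0 points |
| 3 | ±7.5 points |
| 4 | ±10.0 points |

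Check at k = 4 with 14/36 known pregnancies in each arm: if all four unknown treated women are pregnant and no unknown control woman is, (18 − 14)/40 = +10.0 points; the reverse gives (14 − 18)/40 = −10.0 points. These are worst-case limits, not expected bias.

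**Step 5: never-starters.** Assume 16 ongoing pregnancies among 40 randomised, 16/40 = 40.0%. Omitting one non-pregnant never-starter gives 16/39 = 41.0%; omitting two gives 16/38 = 42.1%.

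**Step 6: sampling error.** At an assumed 40% in both arms, the 95% half-width for the difference is 1.96 × √(2 × 0.4 × 0.6 / 40) = 0.215, or about ±21 points.

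**Step 7: a limit of the usual scoring convention.** The plan has no rule that unknown outcomes count as not pregnant; the fix below introduces one, so its behaviour should be known. With 4 unknown in control, 1 unknown in treatment and the same true rate r in both arms, the observed rates are r × 36/40 and r × 39/40, a spurious difference of r × 3/40. That is 2.3, 3.0 and 3.8 points at r = 30%, 40% and 50% (36.0% against 39.0% at r = 40%). The sign reverses if the imbalance does, and with equal unknowns the shift is zero.

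**The case against.** The best defence is that the sections do not contradict each other. Section 5.4 never says that follow-up ends at exit. The follow-up rule in section 5.8.7 turns on the pregnancy test and not on adherence, the visit schedule has no branch for exited women, and deviation is listed separately from loss to follow-up. Read literally, a deviating woman with a positive test is still followed to 12 weeks. FAS membership is fixed by definition, and the only exclusion for deviations, from the per-protocol set, rests on violations defined before lock. Requiring at least one treatment is a common modified intention-to-treat choice. The study calls itself a pilot and recruits at one centre, where outcomes may be easy to trace.

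Much of this stands. A reader might infer that section 5.4 forbids follow-up after exit, or that exited women are dropped from the primary denominator. The documents support neither: the first is left open, and section 7.1 points against the second.

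What remains is that no passage says collection continues, while the placing of deviation beside dropping out invites the opposite practice. The pre-lock definition of major violations governs the per-protocol set only; it does not settle what exit means or how an unknown FAS outcome is scored. Stating the at-least-one-treatment condition openly does not make the set intention to treat when women know their allocation before starting.

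**Conclusion.** The point holds as a missing provision that leaves section 5.4 unreconciled with sections 7.1 and 7.2, together with an FAS that falls short of the principle it cites. It should be fixed, but it does not invalidate the design.

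The size and direction of any bias cannot be derived from the documents. The illustrations rest on assumed exit counts and, for never-starters, on an assumed 40% rate. They are smaller than the sampling error of a trial of this size. The case for acting is that the change is cheap and that a pregnancy outcome not sought at the time may be hard to recover later. The clinical criteria for cancelling a cycle are not in question.

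**What to change.** 1. In section 5.4, state that deviation and cancellation are recorded as events and do not end outcome collection. Seek the 12-week outcome of the study cycle (fresh or first thawed transfer) for every randomised woman who has not withdrawn consent to follow-up.
2. In sections 7.1 and 7.2, make all randomised women, analysed as allocated, the primary analysis set.
3. Count a study cycle with no retrieval, or with neither a fresh nor a first thawed transfer, as no ongoing pregnancy. Count unknown outcomes as not pregnant, and add a best/worst-case sensitivity analysis. Fix these rules before outcome data are reviewed under section 7.4.4.

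The cost is a few sentences, a few extra follow-up contacts, and slightly lower reported rates. The scoring convention can itself shift the result when unknowns are unequal between arms, so it needs the sensitivity analysis and is no substitute for obtaining the outcome.

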### 5.5 The measurement of research results

Primary indicator: the ongoing pregnancy rate at 12 weeks' gestation.

Secondary indicators: the number of oocytes retrieved, the normal fertilization rate and the rate of high quality embryos, implantation rate, clinical pregnancy rate, and early miscarriage rate.

Randomization: randomized envelope method is used in the study. Random sequence is firstly generated by an independent statistician, secondly the grouping is randomized according to

random number and put into an opaque sealed envelope by the independent personnel, at last the investigator divides the subjects in line with the sealed envelope.

Random ratio: 1:1

Grouping: the treatment group takes RECO-18 while the control group takes the multi-vitamins.

#### 5.6 Informed consent

Before the initiation of study, the informed consent form (ICF) should be used to inform the potential subjects of benefits and risks in simple language. ICF should specify that the informed consent is signed voluntarily, and the potential benefits and risks associated with study are specified, and subjects may drop out from the study at any time.

#### 5.7 Ethics

The study process and informed consent acquisition should comply with Helsinki Declaration. This study has been approved by the Medicine Ethics Committee of Sun Yat-sen Memorial Hospital of Sun Yat-sen University. Every subject should sign the informed consent. The informed consent copy, and contact information of the investigator and Medicine Ethics Committee must be provided to the subjects.

#### 5.8 Research method

5.8.1 Collection of basal data: age, infertility length, weight, and body mass index (BMI).

5.8.2 Collection of basal endocrine indexes: follicle stimulating hormone (FSH), luteinizing hormone (LH), estradiol, testosterone, dehydroepiandrosterone sulfate (DHEAS), sex hormone binding globulin (SHBG), and anti-müllerian hormone (AMH).

5.8.3 Collection of biochemical indexes: alanine aminotransferase (ALT), aspartate aminotransferase (AST), creatinine, total cholesterol (TC), triglycerides (TG), high-density lipoprotein (HDL), low-density lipoprotein (LDL), apolipoproteins B (ApoB), high-sensitivity C-reactive protein (Hs-CRP), fasting glucose, and fasting insulin.

5.8.4 Ultrasound examination: bilateral ovarian size, follicle number, and antral follicle count (AFC);

5.8.5 Controlled ovarian stimulation and IVF/ICSI:

a. Controlled ovarian stimulation

Gonadotropin-releasing hormone (GnRH) antagonist protocol: gonadotropin (Gn) 100 IU to 250 IU/day is individually administered to stimulate follicular growth on the 2nd to 4th day of menstruation. GnRH antagonist is added when dominant follicle reaches  $\geq 14$ mm in diameter and LH level is  $\geq 10$ IU/L, and is stopped until the day of human chorionic gonadotropin (HCG) administration.

GnRH agonist long protocol: in the midluteal phase of the menstrual cycle confirmed by ultrasound or hormone test or after 2 weeks of oral contraceptive use, pituitary downregulation is achieved by injection of 0.93-1.87mg long-acting GnRH agonist. 14 to 21 days later, vaginal ultrasound and blood hormone tests are performed to evaluate the complete downregulation of the

pituitary gland. Ovarian stimulation is initiated with Gn 100U-250U/day, and adjustment of Gn dosage is performed according to serum hormone level and follicle growth.

b. Trigger: recombinant HCG of 250ug is administered to induce oocyte maturation when at least two follicle  $\geq 18$ mm or three follicles  $\geq 17$ mm or four follicles  $\geq 16$ mm in diameter.

c. Oocyte retrieval, luteal support and embryo transfer: oocyte recovery is performed 34 to 38 hour after the trigger. Luteal support is provided on the day of oocyte retrieval, with vaginal micronized progesterone capsules (600mg/day) combined with oral dydrogesterone (30mg/day) until the pregnancy test. With the use of conventional IVF or ICSI fertilization, 1 to 2 cleavage stage embryos or day 5 blastocysts are transferred to the uterus, and the rest available embryos are cryopreserved.

d. If fresh embryo transfer is cancelled due to medical reasons, pregnancy outcome of the first thawed embryo transfer is collected. The endometrial preparation, thawed embryo transfer and luteal support are based on the routine operation.

#### 5.8.6 Collection of discarded sample:

a. Follicular fluid is collected during oocyte retrieval.

b. The cumulus oocyte complex (COCs) is put into hyaluronidase by the digestion for 10 to 30 seconds to remove the cumulus cells, and the oocytes are picked up and cumulus cells are collected.

#### 5.8.7 Follow-up:

A total of three visits are followed up during the treatment procedure.

a. At the 14th day after embryo transfer: to record urinary pregnancy test, serum HCG and progesterone level.

If pregnancy test is positive, the following follow-up continues, otherwise it discontinues.

b. Four to five weeks after embryo transfer: to perform transvaginal ultrasound. Clinical pregnancy is defined as a gestational sac and fetal heart beat detected on ultrasound.

c. At 12 weeks' gestation: to perform ultrasound. Ongoing pregnancy is defined as live fetuses detected on ultrasound.

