**Plan of follow-ups:**

	Screening and randomization	IVF/ICSI treatment		Follow-up		
	V1	V2	V3	V4	V5	V6
	Before IVF/ICSI treatment	IVF/ICSI treatment cycle	Thawed ET cycle	2 weeks after ET	4-5 weeks after ET	12 weeks of gestation
Informed consent	√					
Eligibility Criteria	√					
Personal information	√					
History	√					
Companied medication	√	√	√	√	√	√
Physical examination	√					
Vital signs	√	√	√			
Sex hormones	√	√	√			
Ultrasound	√	√	√		√	√
Complication and adverse events		√	√	√	√	√

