## 6. Safety evaluation

6.1 Adverse events: Any adverse medical events occurring during the study period are defined as adverse events, such as drug reactions, adverse reactions associated with ovarian stimulation, complications associated with pregnancy, and other discomfort complaints

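### Scheduled adverse-event collection after day 14 post-transfer reaches only women with a positive pregnancy test, and no visit is timed from retrieval or last intake, so the arms have no common safety window

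*Combined protocol and SAP*

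**What the plan says.** - **Stopping rule.** Section 5.8.7 has three follow-up visits. The first is described as "At the 14th day after embryo transfer: to record urinary pregnancy test, serum HCG and progesterone level". The rule that follows it is "If pregnancy test is positive, the following follow-up continues, otherwise it discontinues". The other two visits are "Four to five weeks after embryo transfer: to perform transvaginal ultrasound" and the scan at 12 weeks: "At 12 weeks' gestation: to perform ultrasound. Ongoing pregnancy is defined as live fetuses detected on ultrasound".
- **Where adverse events are collected.** In the Plan of follow-ups table, the row "Complication and adverse events" is ticked at V2 (IVF/ICSI cycle), V3 (thawed transfer cycle), V4 (2 weeks after transfer), V5 (4 to 5 weeks after transfer) and V6 (12 weeks of gestation).
- **Women without a fresh transfer.** Section 5.8.5 d: "If fresh embryo transfer is cancelled due to medical reasons, pregnancy outcome of the first thawed embryo transfer is collected". No date or limit is given for that transfer. Section 5.4 makes a cycle cancelled for low response or premature ovulation a reason for exit, and describes no safety contact afterwards.
- **Exposure.** Under section 4, study product stops on the day of oocyte retrieval, and the control product is taken over the same period.
- **What counts, and how it is summarised.** Section 6.1: "Any adverse medical events occurring during the study period are defined as adverse events". It includes complications of pregnancy and does not say when the study period starts or ends. Section 6.2 requires serious events to be reported within 48 hours. Section 6.3 names adverse events in the two groups as the safety indexes. Section 7.3 plans descriptive summaries, with case numbers and percentages for classified laboratory and vital-sign values, and leaves the form of the rest open.

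**The concern.** Product intake ends at retrieval, but every scheduled contact after the treatment cycle is tied to a transfer or to gestational age, and the later ones need a positive test. How long a woman is asked about adverse events thus depends on something that happens after randomisation and that the product is meant to change.

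Two consequences follow. First, counts by arm would cover unequal periods whenever the arms differ in positive tests, and a superiority trial on pregnancy expects such a difference if its hypothesis is true. An arm with more pregnancies is observed for longer and also has more women who can have a pregnancy complication, so it can look less safe at the same underlying event rate. An arm with fewer pregnancies can look safer. Second, non-serious events soon after retrieval have no scheduled point of collection in women who do not go on to a fresh transfer, although section 6.1 lists reactions to ovarian stimulation among the events to be captured.

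**Working it through.** The plan states no figure on this point, so there is none to reproduce. The check sets the visit rules side by side and then does calendar arithmetic.

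**1. Scheduled adverse-event contacts after V2, by path**

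| Path | Contacts after V2 |
|---|---|
| Fresh transfer, test positive | V4, V5, V6 |
| Fresh transfer, test negative | V4 only |
| Fresh transfer cancelled, thawed transfer later | V3 (undated), then V4, and V5 and V6 if positive |
| No transfer at all, or exit on a cancelled cycle | None described |

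**2. Length of follow-up from transfer**

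Inputs from the plan: test at day 14 after transfer; last visit at 12 weeks' gestation, which is 84 days. Assumption: gestational age at transfer is 14 days plus embryo age, with day-3 or day-5 embryos.

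- Day-3 embryo: 84 − (14 + 3) = 67 days from transfer to V6. Extra time 67 − 14 = 53 days; ratio 67/14 = 4.8.
- Day-5 embryo: 84 − (14 + 5) = 65 days. Extra time 65 − 14 = 51 days; ratio 65/14 = 4.6.
- Counted from retrieval with a fresh transfer, the negative-test visit falls at 14 + 3 = 17 or 14 + 5 = 19 days, and V6 at 67 + 3 = 65 + 5 = 70 days.

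**3. Mean post-transfer time by arm**

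Formula: mean days = 14 + p × extra days, where p is the proportion with a positive test. The plan gives no value of p, so these are assumptions. The formula treats every test-positive woman as followed to V6, which ignores early miscarriage.

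| p, control v treatment | Day-3 embryo (extra 53) | Ratio | Day-5 embryo (extra 51) | Ratio |
|---|---|---|---|---|
| 30% v 30% | 29.9 v 29.9 | 1.00 | 29.3 v 29.3 | 1.00 |
| 30% v 40% | 29.9 v 35.2 | 1.18 | 29.3 v 34.4 | 1.17 |
| 40% v 50% | 35.2 v 40.5 | 1.15 | 34.4 v 39.5 | 1.15 |
| 40% v 55% | 35.2 v 43.15 | 1.23 | 34.4 v 42.05 | 1.22 |
| 50% v 65% | 40.5 v 48.45 | 1.20 | 39.5 v 47.15 | 1.19 |

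**4. Counting the time on product as well**

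Take 60% (treatment) v 45% (control) and the midpoint of 52 extra days. Post-transfer time is 14 + 0.60 × 52 = 45.2 days v 14 + 0.45 × 52 = 37.4 days, ratio 1.21. Now add about 44 days from first intake to transfer (assumed: 40 days of intake plus 3 to 5 days to transfer). Totals are 89.2 v 81.4 days, ratio 1.10. Shared time before transfer thus roughly halves the relative imbalance.

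**The case against.** In support of the plan as it stands, one can say the following.

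- **Section 5.8.7 is about pregnancy follow-up.** Its visits list only pregnancy tests, hormone levels and scans, and V6 by its heading cannot apply to a woman who is not pregnant. That adverse-event collection also ends is an inference. This stands in part: the text does not say that reporting of events ceases. But the only scheduled collection after day 14 sits at the visits that are stopped, and nothing limits the rule to pregnancy follow-up.
- **Serious events are not tied to visits.** True: section 6.2 covers them when they occur. It does not provide for asking about non-serious events, and the undefined study period leaves open when the duty ends.
- **The events of main interest come early.** Section 6.3 names gastrointestinal reactions and allergies. Intake stops at retrieval, and test-negative women with a fresh transfer are still seen 17 to 19 days later. This stands; the imbalance bears mainly on late and pregnancy-related events.
- **Pregnancy complications need a pregnancy under any window.** True, which is why they need a separate table as well as equal follow-up for everything else.
- **Safety reporting in this 80-woman pilot is descriptive.** True, and no test between arms is planned for safety. Descriptive counts by arm will still be read as a comparison.

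Three stronger readings are tempting, and the documents do not support them. A reader might infer that all women without a fresh transfer have no safety contact after retrieval; the visit table gives thawed-transfer women V3 and then V4 onwards. A reader might infer that follow-up depends on the primary outcome; the trigger is the day-14 test, whereas section 5.5 has "Primary indicator: the ongoing pregnancy rate at 12 weeks' gestation", and a woman who miscarries after a positive test is followed past day 14 yet fails the primary outcome. A reader might infer that women whose fresh transfer is cancelled are those most prone to stimulation reactions; section 5.8.5 d says only that the reasons are medical.

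**Conclusion.** The point holds in this limited form. As written, the scheduled adverse-event visits after day 14 take place only in test-positive women; no visit is timed from retrieval or last intake; women who never reach a transfer have no described contact after V2; and no common window is set for counting events.

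For an individual woman, the last scheduled contact differs by 51 to 53 days, given the usual dating of a day-3 or day-5 transfer. For the arms, the size depends wholly on assumed positive-test rates. It is zero at equal rates, about 15 to 23% of mean post-transfer time for differences of 10 to 15 points, and roughly 10% in the 60% v 45% case when the assumed 44 days before transfer are included. These ratios describe observation time, not a predicted excess of events, and early miscarriage would alter them.

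The primary efficacy analysis is not affected. This is an inexpensive improvement to the safety comparison, best made before follow-up begins because missed contacts cannot be reliably recovered later.

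**What to change.** - **Section 6.1:** define the adverse-event period for every treated woman as running from first intake to a fixed number of days after retrieval or last intake, for example 30. The number is the sponsor's choice. It should apply whatever the test result, and to women with no transfer or a cancelled cycle.
- **Plan of follow-ups table:** add a closing telephone contact at the end of that period for women not otherwise seen. With a 30-day window, V5 already serves test-positive women with a fresh transfer, since it falls 28 + 3 = 31 to 35 + 5 = 40 days after retrieval. The call is for test-negative women, women awaiting a thawed transfer, and women with no transfer.
- **Section 5.8.7:** state that a negative test ends pregnancy follow-up only.
- **Sections 6.3 and 7.3:** compare the arms on the common window, and tabulate pregnancy complications separately, per pregnancy and per randomised woman.

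The cost is at most one telephone call per woman not otherwise seen, in a trial of 80, plus the wording changes. The change concerns data collection only and leaves treatment as it is.
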